4.4.2 Immunizations

4.4.2.1 Tetanus Toxoid Vaccine

TT vaccine is indicated for the prevention of tetanus. The TT vaccine will be administered as part of the combined adsorbed vaccine with diphtheria (Td/DT) and/or acellular pertussis (DTaP/Tdap). In this study, TT adsorbed vaccine is being used to assess whether OCR affects antibody production to an antigen to which individuals have pre-existing immunity.

Group A patients will receive a TT-containing adsorbed vaccine (0.5 mL) as an intramuscular (IM) injection in the deltoid muscle at Day 85/Week 12.

Group B patients will receive a TT-containing adsorbed vaccine ([0.5 mL]) as an IM injection in the deltoid muscle on Day 1/Week 1.

4.4.2.2 23-Valent Pneumococcal Polysaccharide Vaccine

The 23-PPV is indicated for immunization against pneumococcal disease caused by those pneumococcal serotypes included in the vaccine. It has been chosen for this study to assess antibody production for a clinically relevant antigen that is unknown to most individuals. The 23-PPV will be administered in the deltoid muscle as a single IM injection.

Group A patients will receive the 23-PPV vaccine (0.5 mL) as an IM injection in the deltoid muscle at Day 112/Week 16.

Group B patients will receive the 23-PPV (0.5 mL) as an IM injection in the deltoid muscle at Day 28/Week 4.

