4.4.2.5 Seasonal Influenza Vaccine

The influenza vaccine is indicated for immunization against influenza caused by the influenza strains included in the vaccine. The inactivated (or recombinant) vaccine has

been chosen for this study to assess antibody production for a commonly used clinically relevant antigen.

Group A2 patients can receive the influenza vaccine at any time between Day 85/Week 12 and Day 140/Week 20.

Group B patients will receive the influenza vaccine as an IM injection in the deltoid muscle at any time between Day 1/Week 1 and Day 84/Week 12. If a patient needs to receive the influenza vaccine after Week 12, the optional OCR infusion must be delayed.

Group A1 patients can receive the influenza vaccine at any time at the discretion of the investigator.

Refer to the label for dosing and administration guidance.

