6. STATISTICAL CONSIDERATIONS AND ANALYSIS PLAN

6.1 DETERMINATION OF SAMPLE SIZE

Approximately 100 patients will be enrolled using a 2:1 randomization ratio into active (Group A) and control (Group B) groups. For the positive response to TT-containing adsorbed vaccine measured 8 weeks after the administration of vaccine, if both the control and active (OCR) groups have 70% response rates, the expected half width of the resulting 95% CI of the difference of two response rates is 0.201.

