Appendix 1 Schedule of Assessments: Table A (cont.)

- 20 **CD4 count:** will be measured separately at screening, and be included in the flow cytometry (FACS) panel at all following visits including every q22-week visit in order to inform eligibility/re-treatment criteria. Other re-treatment labs will be measured as part of IgG and routine safety labs (see item 21 and 22).
- 21 **Flow cytometry:** including CD19 and other circulating B-cell subsets, T-cells (including CD4 cells), NK cells and other leukocytes. On the infusion days, samples should be collected prior to infusion of methylprednisolone.
- 22 **Routine safety labs.** On infusion visits, all urine and blood samples should be collected prior to the infusion of methylprednisolone. At other times, samples may be taken at any time during the visit.
- 23 All patients will receive **prophylactic treatment** with 100 mg of methylprednisolone IV 30 minutes prior to, and an IV or oral antihistamine such as diphenhydramine 50 mg 30–60 minutes prior to OCR infusions. In patients where methylprednisolone is contraindicated, corresponding doses of other IV steroids (e.g., dexamethasone) may be used as premedication. It is also recommended that patients receive an analgesic/antipyretic such as acetaminophen/paracetamol (1 g), 30–60 minutes prior to OCR infusions.
- 24 **Study drug administration:** The investigator must review the clinical and laboratory re-treatment criteria prior to re-dosing patients with study drug at Day 168 (Week 24) and prior to any subsequent OCR infusion.
- 25 Influenza vaccine and post-vaccination assessment for Group A2 only. Influenza can be administered between Weeks 12–20. Post-vaccine assessments must be done after 4 weeks. For patients in Group A2 who are due to receive the influenza vaccine during their country-specific influenza vaccine blackout period, administration of the vaccine should be given prior to the start of this blackout period. Group A1 patients can receive the influenza vaccine at any time at the discretion of the investigator.
- 26 M=Sample to be taken prior to immunization on days when vaccines are administered. On infusion visits, all urine and blood samples should be collected prior to the infusion of methylprednisolone. At other times, samples may be taken at any time during the visit.
- 27 Group A1 only.

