4.1.3 Safety Population

The Safety Population will include all patients who received any ocrelizumab or any vaccine. Randomized patients who received an incorrect medication or vaccine rather than the one they were assigned to will be summarized in the group according to the medication or vaccine actually received.

All safety outcome measures will be analyzed using the Safety Population.

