4.6 SAFETY ANALYSES

For safety analyses, data will be presented for Groups A1 and A2 separately as well as for Group A (Groups A1 and A2 combined) and B.

All summaries of safety data will be based on the Safety Population.

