For each treatment group, the incidence count for each adverse event PT will be defined as the number of patients reporting at least 1 treatment-emergent occurrence of the event. The incidence rate will be calculated as the incidence count divided by the total number of patients in the population. Each table will also present the overall number of patients experiencing at least 1 adverse event and the total number of adverse events reported (multiple occurrences of the same adverse event in one patient will be counted only once at the most extreme intensity). For adverse events leading to death, the most extreme intensity will be overwritten by Grade 5 (death).

Serious adverse events will be defined as all serious adverse events, which includes serious MS relapses and serious IRRs. Serious adverse events will be summarized for each treatment group by SOC and PT, and presented in a data listing. Additionally, the most frequent serious adverse events ($\geq 1\%$) will be presented by PT for each treatment group. A separate listing with relapses considered as serious adverse events will be presented. Related adverse events and serious adverse events will be summarized by SOC and PT for each treatment group and separately for adverse events related to (or suspected to be related to) treatment with each of the following:

- Ocrelizumab
- Methylprednisolone
- KLH
- Tetanus and diphtheria vaccine
- Tetanus, diphtheria, and pertussis vaccine
- 23-PPV
- 13-PCV
- Influenza vaccine

Concomitant treatments for adverse events (excluding IRRs and MS relapses) will be summarized by class and PT. Also concomitant treatments starting during the ISP or during the SFU Period following the ISP will be summarized by class and PT.

Adverse events and serious adverse events will be summarized by intensity (most extreme intensity) and overall, by SOC and PT. Additionally, adverse events of intensity grades 3, 4, or 5 (most extreme intensity) will be summarized by intensity and overall, by SOC and PT.

All patient deaths during the study (all study periods) will be included in a data listing.

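### Vaccine-related adverse event rates are divided by everyone in the group, not by recipients of the product; this mainly lowers the Group A overall influenza rate and the Td and Tdap rates

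*SAP*

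**What the plan says.** SAP 4.6.2.1 defines the adverse event rate for every summary of the Immunization Study Period (ISP): "The incidence rate will be calculated as the incidence count divided by the total number of patients in the population". The population is the one in SAP 4.1.3: "The Safety Population will include all patients who received any ocrelizumab or any vaccine". Section 4.6.2.1 then asks for related adverse events and serious adverse events by treatment group, "separately for adverse events related to (or suspected to be related to) treatment with each of the following". The list that follows includes KLH, Td, Tdap, 23-PPV, 13-PCV and influenza vaccine. No separate denominator is given for these tables. On columns, SAP 4.6 says that "data will be presented for Groups A1 and A2 separately as well as for Group A (Groups A1 and A2 combined) and B".

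Who receives what is set by the protocol:

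- **Influenza vaccine:** scheduled for all of Group B (Protocol 4.4.2.5). Within Group A, Appendix 1, Table A, note 25 says "Influenza vaccine and post-vaccination assessment for Group A2 only". Section 4.4.2.5 adds that "Group A1 patients can receive the influenza vaccine at any time at the discretion of the investigator".
- **13-PCV:** A1 only (Protocol 4.4.2.4).
- **Tetanus:** a Td/DT or a DTaP/Tdap product, under the same rule in both arms (Protocol 4.4.2.1; Appendix 1, note 28 to Tables A and B). The share of each product is not stated.
- **23-PPV and KLH:** all patients in both arms.

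Group A is first vaccinated at Week 12, after ocrelizumab. Group B is first vaccinated on Day 1 (Protocol 3.1). SAP 4.6.1 summarizes exposure to ocrelizumab only.

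**The concern.** A rate of reactions to a product should be taken over the people who received it. Under the stated rule, non-recipients enter the denominator and can never enter the numerator, so the printed percentage is the per-recipient rate multiplied by the share of the column that was exposed. Where that share differs between columns, equal tolerability prints as unequal rates.

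Events associated with the study immunizations are a named safety outcome (Protocol 3.4.4; SAP 2.2.4). The randomized contrast is Group A overall against Group B, because A1 and A2 were formed non-randomly (SAP 2 and 4.4.2.2). For influenza vaccine, that is the pair of columns with unequal exposure. A reader could take the lower figure under ocrelizumab as better vaccine tolerability when it only reflects who was vaccinated.

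**Working it through.** **Inputs from the documents.** Protocol 6.1: "Approximately 100 patients will be enrolled using a 2:1 randomization ratio into active (Group A) and control (Group B) groups". Protocol 3.1: Group A is split 50/50, with about 33 in A1, and about 33 but at least 30 in A2.

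**The plan's own figure.** 100 x 2/3 x 0.5 = 33.3 per subgroup, which agrees with the stated 33.

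**Assumed inputs, not in the documents.** The true related-event rate per recipient, r, is taken as equal in both arms, from 5% to 40%. Also assumed are the share u of A1 patients who take influenza vaccine, the share s of patients given Td rather than Tdap, and the fraction of Group A lost before Week 12.

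**Formula.** Displayed rate = r x (recipients in column / patients in column).

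**Influenza, Group A overall, no A1 uptake.** The factor is 33/66 = 0.50, or 30/67 = 0.45 at the minimum A2 size. In Group B it is 33/33 = 1.00 if all are vaccinated as scheduled.

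| r in both arms | A overall at 33/66 | A overall at 30/67 | Group B |
|---|---|---|---|
| 5% | 2.5% | 2.2% | 5% |
| 10% | 5% | 4.5% | 10% |
| 20% | 10% | 9.0% | 20% |
| 40% | 20% | 17.9% | 40% |

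**Influenza, with A1 uptake.** The factor is (33 + 33u)/66, which gives 0.50 at u = 0, 0.75 at u = 0.5 and 1.00 at u = 1. At r = 20% the Group A overall column shows 10%, 15% and 20%.

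**Influenza, A2 column.** The factor is 1.00 if all of A2 is vaccinated, so 20% shows as 20%, level with Group B.

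**13-PCV.** The factor is 1.00 in A1 and about 0.50 in A overall. Group B has no recipients, so there is no comparison to distort.

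**Td and Tdap.** The factor is s for Td and 1 - s for Tdap, in every column including Group B. If s is the same in both arms, the dilution is equal. By chance alone at s = 0.5, the standard error of the difference in share is sqrt(0.25 x (1/66 + 1/33)) = 0.107. The 95% range is 1.96 x 0.107 = about 21 points of share, or 0.21 x 20% = about 4 points on a true 20% rate.

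**Leavers before Week 12.** A Group A patient who received ocrelizumab and left before Week 12 is in the Safety Population with no study vaccine. If 3%, 5% or 10% do so, every vaccine rate in Group A overall is multiplied by a further 0.97, 0.95 or 0.90, and likewise in A1 and A2 if the loss falls equally on them. At r = 20% a fully scheduled column shows 19.4%, 19.0% or 18.0%. A Group B patient who leaves before any vaccine is not in the Safety Population at all, so this loss has no counterpart there.

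**The case against.** The strongest reply is that the proper influenza contrast is already in the table. A1 and A2 have their own columns, SAP 4 labels them by the vaccine they receive, and SAP 4.4.2.4 says that influenza response needs A2 against B. On this view only the combined column misleads, and its make-up is known. This largely stands for influenza and for 13-PCV. It does not help the Td and Tdap tables, it does not correct for leavers before Week 12, and it leaves the A1 influenza column with an unknown number of recipients.

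A second reply is that the number vaccinated could be recovered. SAP 4.6.2.1 plans a summary of concomitant treatments starting in the ISP, and Protocol 4.6.1 counts preventative vaccines as concomitant medication. That is a possible source, but the SAP does not say that it covers the study vaccines, and it would not change the printed adverse event percentages.

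A third reply is that these tables are descriptive: no test or between-group difference is specified for adverse events, and all events are listed. That stands, and it limits the consequence.

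A reader might infer more than the documents support, in three ways:

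- **That every vaccine-related rate is diluted unequally between the arms by the choice of product.** Both arms follow the same tetanus rule and nothing ties the product to the group, so unequal Td or Tdap dilution is possible but not shown.
- **That 13-PCV biases a comparison with control.** Group B never receives it.
- **That the Group A influenza rate is halved outright.** That is the figure with no A1 uptake; with discretionary vaccination the factor may be anything up to 1.00.

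**Conclusion.** The point holds in a limited form. The SAP states a denominator that includes non-recipients and applies it to product-specific tables.

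- **Influenza:** the Group A overall rate is multiplied by about 0.45 to 0.50 if no A1 patient is vaccinated, 0.75 if half are (33/33 split) and 1.00 if all are, against about 1.00 in Group B. The A2 and B columns are right if all planned vaccinations are given.
- **Td and Tdap:** percentages understate per-recipient rates in every column where both products are used. A bias between arms is not established.
- **13-PCV:** by design, diluted only in the Group A overall column.
- **All vaccines:** Group A patients lost between ocrelizumab and Week 12 lower the rates on the Group A side only. The size depends on a loss rate that the documents do not give.

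The displayed percentages rest on assumed reaction rates; the influenza factors rest on the planned group sizes and on A1 uptake. The primary endpoint is unaffected. This is a minor correction to descriptive safety tables, worth making because readers of the planned tables could not reliably correct the figures themselves.

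**What to change.** In SAP 4.6.2.1, for each vaccine-related and KLH-related adverse event and serious adverse event table, set the denominator to the Safety Population patients in that group who received at least one dose of that product in the ISP, and print that number in the column header. For influenza vaccine, compare A2 recipients with Group B recipients and show A1 recipients separately. In SAP 4.6.1.1, add a count of recipients by product and group. Equal true rates then display as equal, for example 20% v 20%.

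The cost is SAP wording and some table programming. Vaccine administration is already recorded, so no new data are needed. The percentages rest on fewer patients and are slightly less precise.

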Patients in Group A are to first receive OCR (Day 1/Week 1 [Dose 1 Infusion 1] and Day 15/Week 2 [Dose 1 Infusion 2]), and 12 weeks post-OCR treatment, are to receive a similar immunization course to Group B. Group A will be further subdivided into two groups to evaluate the effectiveness of a booster 13-PCV vaccination or of influenza vaccination.

For the primary objective and for secondary objectives 1 and 3, Group A (active) will be compared with Group B (control).

To determine the outcomes of secondary objectives 2 and 4, patients in Group A will be split into two groups with 50% of patients in each group (Groups A1 and A2). Patients will be assigned to either Group A1 or A2:

- Group A1 will receive booster 13-PCV (approximately 33 patients)
- Group A2 will receive the influenza vaccine (approximately 33 patients but a minimum of 30 patients).

A minimum of 30 patients will be assigned to Group A2 during the first influenza season. If a minimum of 30 patients (a maximum of 33) are assigned to Group A2 and receive the first year's influenza vaccine, all remaining patients in Group A will be assigned to Group A1 and receive the 13-PCV booster. If less than 30 patients have been assigned to Group A2 during the first influenza season, further patients assigned to Group A2 will have influenza vaccine visits during the subsequent influenza season (i.e., when the next year's vaccine becomes available).

The primary and secondary humoral immunity and immunophenotyping outcomes are to be measured by flow cytometry and quantitative Ig measurements.

Approximately 30–35 centers will participate in the study in the United States/North America. This study consists of up to five study periods:

- Screening Period
- Immunization Study Period

Group A: Immunization Study Period and OCR treatment starts at Day 1/Week 1.

Patients will receive 300 mg of open-label OCR on Day/Week 1 (Dose 1 Infusion 1) and Day 15/Week 2 (Dose 1 Infusion 2). Patients in Group A will be split and be assigned to either Group A1 (booster 13-PCV) or Group A2 (influenza vaccine). At Day 85/Week 12 patients will start to receive immunizations and undergo post-immunization assessments. For all patients in Group A, the Immunization Study Period will end on Day 169/Week 24.

Group B: Patients will not receive OCR. At Day 1/Week 1, patients will start to receive immunizations and undergo post-immunization assessments. For Group B, the Immunization Study Period will end at Day 84/Week 12.

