4.6.1 Exposure to Study Medication (Ocrelizumab)

4.6.1.1 Exposure to Ocrelizumab during the ISP

Patients will be considered to have received a dose of ocrelizumab treatment if at least one part of one infusion of that dose (i.e., either Day 1 or 15 for dual infusions) was given.

Treatment duration for ocrelizumab-treated patients in the ISP will be calculated as the date of the last recorded observation during the ISP (the date reported on the ISP Completion/Early Discontinuation electronic Case Report Form [eCRF]) minus the date of first dose of ocrelizumab. If protocol requirements are followed exactly, this duration should be 168 days (24 weeks) for patients who do not withdraw/discontinue early.

Exposure to ocrelizumab for patients in Groups A1, A2, and A (Groups A1 and A2 combined) during the ISP will be summarized as follows:

- Dose received on Day 1: number and percentage of patients who received ocrelizumab dose
- Dose received on Day 15: number and percentage of patients who received ocrelizumab dose

- Total cumulative dose of ocrelizumab (mg; Day 1 + Day 15): summary statistics, including mean, median, SD, minimum, and maximum
- Receiving <80% and ≥80% of the planned infusion on Day 1: number and percentage of such patients
- Receiving <80% and ≥80% of the planned infusion on Day 15: number and percentage of such patients
- Pretreatment with steroids on Day 1: number and percentage of patients pretreated on Day 1
- Pretreatment with steroids on Day 15: number and percentage of patients pretreated on Day 15
- Pretreatment with antihistamines on Day 1: number and percentage of patients pretreated on Day 1
- Pretreatment with antihistamines on Day 15: number and percentage of patients pretreated on Day 15

A listing of information relating to exposure to ocrelizumab will be provided.

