4.6.2.1 Adverse Events during the ISP

Adverse events will be defined as all adverse events, except non-serious MS relapses, but including infusion-related reactions (IRRs) and serious MS relapses. Therefore, those adverse events recorded on the “adverse event” and “infusion-related reaction (IRR)” CRF pages will be included.

For each adverse event recorded, the term entered by the investigator describing the event (the “reported term”) will be assigned a standardized term (the “preferred term”) based on the MedDRA WHO dictionary of terms. All analyses of adverse event data will be performed using the PTs unless otherwise specified.

All adverse events will be mapped to PTs and superclass terms and included in a data listing (a separate listing showing relapse information will also be presented). For all summary tables, the adverse events will be sorted by SOC (in decreasing order of overall incidence) and then by PT (in decreasing order of overall incidence). An adverse event profile summary table will be presented to provide an overview of adverse events reported in the ISP. Additionally, the most frequent adverse events ($\geq 5\%$ in any treatment group) will be presented by PT.

Summaries of adverse events will be generated by summarizing the incidence of treatment-emergent adverse events only. Treatment-emergent events are defined as those adverse events with observed or imputed onset date on or after the start date of study treatment (ocrelizumab or any vaccinations). Only where the most extreme intensity is greater than the initial intensity will events with an onset date prior to the start of study treatment (and with an end date on or after the start of study treatment) be considered treatment-emergent. An adverse event with a completely missing, non-imputed start date will be assumed to be treatment-emergent unless the adverse event has a complete non-imputed end date that is prior to start of study treatment.

Adverse events will be assigned to a dose if the adverse event onset date is on or after the date of the first infusion of that dose but before the first infusion of the next treatment dose. Adverse events that start prior to the first dose and worsen during treatment (i.e., treatment-emergent) will be assigned to the first treatment dose.

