A patient may experience an adverse event that leads to the discontinuation of their study treatment. Discontinuation of study treatment for an adverse event may not necessarily lead to discontinuation from the study because patients can enter the SFU Periods. Only adverse events that led to the discontinuation of study treatment are of interest. Patients who withdraw early from the study because of adverse events will be

Ocrelizumab—F. Hoffmann-La Roche Ltd
26/Statistical Analysis Plan BN29739

Clinical Study Report: ocrelizumab - F. Hoffmann-La Roche Ltd
Protocol BN29739 Report Number 1079337

summarized under disposition. The number of patients who experienced an adverse event that led to discontinuation of study treatment will be summarized by SOC and PT for each treatment group. A listing will be presented showing all adverse events which led to discontinuation of study treatment.

The number of patients who experienced an adverse event that led to modification or interruption of study drug will be summarized by SOC and PT for each treatment group.

A glossary of superclass terms, PTs and verbatim terms for adverse events will be provided. Also a glossary of superclass terms and PTs for adverse events baskets will be provided.

To comply with the reporting requirements of www.clinicaltrials.gov, the following two tabular summaries will be provided for the ISP. For the two summaries below, unlike all other adverse event summaries in this study, multiple occurrences of the same adverse event in an individual are counted separately:

- Non-serious adverse events reported in $\geq 5\%$ of patients in any treatment group will be summarized by SOC and PT. Non-serious relapses will be excluded here. Within each treatment group, the number and percentage of patients reporting such adverse events, and the number and percentage of events reported, will be presented.
- Serious adverse events will be summarized by SOC and PT. Within each treatment group, the number and percentage of patients reporting serious adverse events, and the number and percentage of serious adverse events reported, will be presented. Further, the total number of serious adverse events in each treatment group that were treatment-related, fatal, and treatment-related and fatal will be presented.

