4.6.3.2 Infections and Serious Infections

Infections will be defined from the adverse event data using the MedDRA SOC of “Infections and Infestations”. An infection will be defined as serious if the event is a serious adverse event.

A listing of infections (defined using the MedDRA SOC “Infections and Infestations”) with pathogen information code will be provided. An additional listing will display adverse events from other SOCs with the pathogen information code. Also a listing will display non-serious infections treated with an intravenous anti-infective.

Immunization Study Period

Infections and serious infections will be summarized by SOC and PT. Infections by intensity will be summarized also. If a patient has multiple events, the most extreme intensity will be taken. Infections and serious infections will also be summarized by pathogen type. The number of infections and serious infections per 100 patient-years will be calculated and summarized.

Optional Ocrelizumab Extension

The same summaries will be presented for OOE as for ISP, with the exception of summaries of infections and serious infections by pathogen type.

All Periods

The same summaries will be presented for all study periods as for ISP.

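### The adverse event total counts patient-by-preferred-term pairs, and the same once-only rule, read literally, caps the infection rate per 100 patient-years

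*SAP*

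**What the plan says.** SAP 4.6.2.1 gives each adverse event table two overall figures: the number of patients with at least one event, and a total of events. For the total, "multiple occurrences of the same adverse event in one patient will be counted only once at the most extreme intensity". The unit is the preferred term (PT): "All analyses of adverse event data will be performed using the PTs unless otherwise specified". Patient-level incidence is defined separately: "The incidence rate will be calculated as the incidence count divided by the total number of patients in the population".

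The same section adds two tables for the trial registry, for the ISP only. One covers serious events. The other covers non-serious events that reach 5% of patients in at least one group. For these two, "unlike all other adverse event summaries in this study, multiple occurrences of the same adverse event in an individual are counted separately". SAP 4.6.2.2 and 4.6.2.3 carry the general ISP approach over to the optional ocrelizumab extension (OOE) and to all periods combined.

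SAP 4.6.3.2 derives infections from the adverse event data and then states: "The number of infections and serious infections per 100 patient-years will be calculated and summarized". This applies to the ISP, the OOE and all periods. The section's only rule on repeats belongs to the intensity table: "If a patient has multiple events, the most extreme intensity will be taken". It sets no repeat rule for the rate.

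Follow-up differs by group. Protocol 3.1 says: "For all patients in Group A, the Immunization Study Period will end on Day 169/Week 24". For Group B the same section ends the period at Day 84/Week 12.

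**The concern.** A figure labelled as an event total should count events. This one leaves out every repeat of a term within a patient, although patient-level counts already sit beside it.

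The infection rate matters more. If the numerator takes each term once per patient while the denominator keeps running, the rate falls as follow-up lengthens, even when the true rate is constant. Group A is followed twice as long as Group B in the ISP, so the two rates would be deflated by different amounts. Protocol 5.1.1.2 lists infection as an identified risk of ocrelizumab, mostly mild or moderate and respiratory. Infections of that kind can plausibly recur under one PT.

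SAP 4.6.2 also assigns events from safety follow-up to the period of the previous dose. Under Protocol 4.7.7, Group B patients who never receive ocrelizumab have no such follow-up. This can lengthen Group A's window further. It is not included in the figures under working.

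**Working it through.** **1. Follow-up time.** The SAP's figure for Group A is: "this duration should be 168 days (24 weeks) for patients who do not withdraw/discontinue early". Day 169 − Day 1 = 168 days = 24.0 weeks, so it reproduces. For Group B, Day 84 − Day 1 = 83 days = 11.9 weeks, nominally 12. In years, T_A = 24/52.18 = 0.460 and T_B = 12/52.18 = 0.230.

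**2. Share of events counted.** Suppose one PT occurs as a Poisson process at rate r per patient-year. The expected number of events is m = rT, and the expected capped count is 1 − e^(−m). The share counted is f(m) = (1 − e^(−m))/m. Patient-years are taken as full follow-up, because SAP 4.6.3.2 does not stop the clock at a first event. The documents give no event rate for this trial, so r is an assumption shown over a range.

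For r = 1: f(0.460) = 0.802 and f(0.230) = 0.893. The apparent A:B ratio is 0.802/0.893 = 0.90 when the true ratio is 1.

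| r per patient-year, one PT, equal in both groups | Lost in A | Lost in B | Capped rate per 100 patient-years, A / B | Apparent A:B ratio |
|---|---|---|---|---|
| 0.1 | 2.3% | 1.1% | 9.8 / 9.9 | 0.99 |
| 0.5 | 10.7% | 5.5% | 44.7 / 47.2 | 0.95 |
| 1 | 19.8% | 10.7% | 80.2 / 89.3 | 0.90 |
| 2 | 34.6% | 19.8% | 130.8 / 160.3 | 0.82 |

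**3. Direction.** f falls as m rises, so Group A loses the larger share only when r_A × 24 > r_B × 12, that is, when r_A > r_B/2. With r_B = 1:

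| True A:B ratio | Lost in A | Lost in B | Apparent ratio |
|---|---|---|---|
| 0.4 | 8.7% | 10.7% | 0.41 |
| 0.5 | 10.7% | 10.7% | 0.50 |
| 1 | 19.8% | 10.7% | 0.90 |
| 1.5 | 27.8% | 10.7% | 1.21 |
| 2 | 34.6% | 10.7% | 1.46 |

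**4. Spread over terms.** The cap works per PT. If 1 event per patient-year is divided evenly over five PTs, the losses are 4.5% and 2.3%, and the ratio is 0.955/0.977 = 0.98. Over ten PTs the losses are 2.3% and 1.1%.

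**5. Variation between patients.** With gamma-distributed patient rates of shape k, the expected capped count becomes 1 − (1 + m/k)^(−k). At r = 1 and one PT, the losses are 31.5% against 18.7% for k = 1 (ratio 0.84), and 39.5% against 25.0% for k = 0.5 (ratio 0.81).

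**6. Raw totals.** These are not divided by exposure. With equal true rates, Group A has 24/12 = 2 times as many events per patient. At r = 1 the cap reduces this to 2 × 0.897 = 1.79, so Group A's total per patient still exceeds Group B's.

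**The case against.** The strongest reply has four parts.

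- **The rate may not be capped.** SAP 4.6.3.2 speaks of a number of infections and sets no cap. SAP 4.6.3.3 sets its own counting units for infusion-related reactions, so the remark introducing the registry tables is not a strict global rule. This stands: a reader might infer that the SAP expressly caps the infection rate, and it does not. But nothing in 4.6.3.2 exempts the rate either, and the only general sentence on the matter points to a cap.
- **Most of the ISP burden is reported in full elsewhere.** The registry tables count every serious event and the common non-serious ones. SAP 4.6 shows A1 and A2 separately, at about 33 patients each. Two patients (2/33 = 6.1%) bring a term in, so what drops out is mainly non-serious terms seen in at most one patient per group. Listings of adverse events and infections are also planned. This stands for the ISP. Those tables are not per patient-year, and no equivalent is planned for the OOE or for all periods.
- **One term at 1 per patient-year is high.** Protocol 1.1.3.2 reports 4194 events in 825 ocrelizumab patients over 96 weeks. With full exposure assumed, that is 4194/(825 × 96/52.18), or about 2.8 per patient-year across all terms; whether repeats are included is not stated. So 0.90 is not a central estimate. It is not an upper bound on the distortion either, since higher rates or variation between patients give a larger one.
- **The analysis is descriptive.** SAP 4.4 plans no hypothesis tests for the outcomes, the safety summaries are descriptive, and patient-level incidence is unaffected. This limits the consequence, but it does not make the label right.

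**Conclusion.** The point holds in a limited form. As written, the event total in the main tables is a patient-by-PT count under the wrong label. For infections and serious infections per 100 patient-years the rule is unclear, and the literal reading caps the numerator over full patient-time. On that reading, and with equal true rates, the ISP rate ratio is multiplied by about 0.90 for one PT at 1 per patient-year, 0.95 at 0.5, and 0.98 when 1 per year is spread over five PTs. Variation between patients enlarges the distortion. All of these rest on assumed rates.

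Three stronger readings are tempting, and the documents do not support them:

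- **That the rule always favours ocrelizumab.** It does so only if Group A's true rate exceeds half of Group B's. That is plausible, but it is not shown for this trial.
- **That the raw totals are biased in ocrelizumab's favour.** They are not exposure-adjusted, and the longer ISP raises Group A's total by more than the cap removes.
- **That the OOE gives a biased treated-versus-untreated comparison.** Group B patients who enter the OOE also receive ocrelizumab, so there is no untreated comparator. This SAP covers only the OOE data available at the ISP cutoff. There the cap understates burden, but it does not create a bias against a control.

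**What to change.** - In SAP 4.6.2.1, count every recorded occurrence in the event total. Keep the once-only rule for the number and percentage of patients and for the worst-intensity tables.
- In SAP 4.6.3.2, state that the numerators of infections and serious infections per 100 patient-years count every recorded occurrence, for the ISP, the OOE and all periods.
- Amend the sentence that sets the two registry tables apart from all other adverse event summaries, so that it agrees with both changes.

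The cost is SAP wording and minor programming. No new data are needed: Protocol 5.3.5.4 already has sites enter each recurrence as its own record, and the registry tables already require full counts.
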